7.2.2 Exploratory analyses

The time-varying Cox model of 7.1.1 will be used for estimation, but ITT censoring will be employed.

7.3 To evaluate the vaccine effect on SARS-CoV-2 viral load

Given the early termination, the study is underpowered to look at the vaccine effect on viral load. Therefore a limited, descriptive analysis will be performed. Descriptive statistics for peak viral loads on the cycle threshold (CT) scale among FAS-P acquisitions (censored at outside vaccination) will be tabulated by lab (Corteva vs. UW/Northwell), target (N1 and N2) and arm. Peak viral load will be defined as the minimum observed CT per participant, lab and target. Participants with CT data from both labs will be excluded. Descriptive statistics will include N, mean, minimum, median, quartiles and median. Results are stratified by lab to address potential differences between labs. We will also present the descriptive statistics for the number of days with a positive study PCR (qualitative) per participant among FAS-P acquisitions, broken down by arm.

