2.2 Study Objectives and Endpoints

Primary Objectives	Primary Endpoints
1. To evaluate the efficacy of Moderna COVID-19 Vaccine against SARS-CoV-2 infection (i.e., to evaluate vaccine efficacy against infection or VES).	SARS-CoV-2 infection diagnosed by PCR among participants who were SARS-CoV-2 seronegative at enrollment
2. To evaluate the effect of Moderna COVID-19 Vaccine on peak nasal viral load as a measure of infection and a proxy of infectiousness	Peak viral load in nasal samples from participants diagnosed with SARS-CoV-2 infection among participants who were SARS-CoV-2 seronegative at enrollment
Secondary Objectives	Secondary Endpoints

1. To evaluate the impact of Moderna COVID-19 vaccine on secondary transmission of SARS-CoV-2 infection, using data for the Prospective Close Contact (PCC) cohort and Case-Ascertained Close Contact (CACC) cohort (ie, to evaluate vaccine efficacy against infectiousness or VEI)
	
Number of adjudicated* secondary transmission events in PCC and CACC cohorts from main study participants who were SARS-CoV-2 seronegative at enrollment.
 
*based on questionnaire-based epidemiologic data, antibody and viral dynamics, and viral sequence data

2. To evaluate the efficacy of Moderna COVID-19 Vaccine to prevent serologically confirmed SARS-CoV-2 infection
	
SARS-CoV-2 antibodies to the nucleocapsid protein post visit 3 (month 1), among participants who were SARS-CoV-2 seronegative at enrollment

3. To evaluate vaccine efficacy against COVID-19 disease, (ie, to evaluate VED) using weekly e-diaries and confirmatory PCR testing
	
SARS-CoV-2 infection confirmed by PCR among participants who were SARS-CoV-2 seronegative at enrollment, coincident with the following symptoms:
 
 • at least TWO of the following systemic symptoms: Fever ($\geq 38^{\circ}\text{C}$), chills, myalgia, headache, sore throat, 
OR
 
at least ONE of the following signs/symptoms: cough, shortness of breath or difficulty breathing, new olfactory or taste disorder, clinical or radiographical evidence of pneumonia, thromboembolic event, myocardial infarction, myocarditis, chilblains, or multi-inflammatory syndrome

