3. GENERAL DATA ANALYSIS CONSIDERATIONS

3.1 Analysis Set(s)

Full Analysis Set (FAS): Limited analyses (e.g. participant characteristics at the baseline) will be carried out among all main study participants that satisfy inclusion criteria and enroll in the study.

Full Analysis Set with PCR data (FAS-P): Only FAS participants with study PCR data will contribute acquisition and viral load (ΔVL) endpoint data and will be used as a main study secondary data set to estimate endpoint parameters. FAS-P participants will be further limited to participants enrolled as randomized to estimate vaccine efficacy against infection (VES). This set will be considered a main study secondary data set.

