Baseline SARS-CoV-2 negative set (Main study primary data set): To account for ramping vaccine efficacy (VE), the protocol stipulated that primary analyses would be conducted among all baseline SARS-CoV-2 negative participants, and again among participants in the “Day 29 Negative Set”—the set of participants without seroconversion or PCR-confirmed infection on or prior to second vaccination on Day 29. The intent of this plan was to evaluate effects of the full two-dose vaccine regimen. Given that time of second vaccination is not easily defined in the SoC and Vaccine Declined groups and given that some participants in the Immediate Vaccination group began swabbing and accruing person-time and infection events before first vaccination, primary analyses will instead be conducted among all eligible enrolled baseline SARS-CoV-2 negative participants (Baseline SARS-CoV-2 negative set). All person-time and events will be included, and ramping VE will be accommodated using analyses that estimate vaccine effects according to number of doses received. Baseline SARS-CoV-2 negativity will be defined as PCR negative based on the first resulted (see section 3.2.9 for exclusions) nasal swab and seronegative based on the first qualifying (see section 3.2.8 for exclusions) blood sample closest to the first resulted swab. Note that blood collection for determining baseline serostatus was intended to occur coincident with initiation of swabbing; however, some participants had blood collected well before they began swabbing, and others had blood collected well after the initiation of swabbing. The analysis will summarize the distribution of time between first resulted swab and first blood. Qualifying blood sample closest to the first resulted swab date will be defined as either the closest qualifying blood sample on or before the first resulted swab date (if it exists) or the closest qualifying blood sample after the first resulted swab date (if no qualifying blood sample exists on or before the first resulted swab date). Primary analyses of vaccine efficacy against infection (VES) and of the vaccine effect on viral load (ΔVL) will be conducted among Baseline SARS-CoV-2 negative set participants that were enrolled as randomized.

All primary and secondary analyses will be done according to enrollment group, ie, Immediate Vaccination Group, Standard of Care Group, or Vaccine Declined Group.

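### SAP 7.3 tabulates peak viral load only in FAS-P, so primary endpoint 2 is never produced in the baseline-negative, enrolled-as-randomised set that SAP 3.1 requires

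*SAP*

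**What the plan says.** SAP 2.2 defines primary endpoint 2 as "Peak viral load in nasal samples from participants diagnosed with SARS-CoV-2 infection among participants who were SARS-CoV-2 seronegative at enrollment". SAP 3.1 says that the primary analyses of vaccine efficacy against infection and of the vaccine effect on viral load "will be conducted among Baseline SARS-CoV-2 negative set participants that were enrolled as randomized". The same section says that FAS-P, the full analysis set with study PCR data, "will be used as a main study secondary data set to estimate endpoint parameters".

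SAP 7.3 sits in the section on primary efficacy and effectiveness analyses. It defines the peak as the minimum observed CT and says: "Descriptive statistics for peak viral loads on the cycle threshold (CT) scale among FAS-P acquisitions (censored at outside vaccination) will be tabulated by lab", and also by target and arm. A second table, days with a positive study PCR, uses the same infections and is also broken down by arm. Section 7.3 cites early termination and low power, and limits itself to descriptive statistics.

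On grouping, SAP 3.1 says: "All primary and secondary analyses will be done according to enrollment group". On the build-up of protection, it says that "ramping VE will be accommodated using analyses that estimate vaccine effects according to number of doses received". It also records that some Immediate Vaccination participants swabbed and had infections before their first dose.

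**The concern.** Peak viral load is one of two primary objectives, and 7.3 holds the SAP's only analyses of viral load. Those analyses use a wider population than the endpoint definition and SAP 3.1 prescribe. Peak viral load without regard to baseline serostatus is secondary objective 5, so the planned table answers that secondary objective and leaves the primary one unanswered.

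Infections in people with earlier infection, or with unknown baseline status, may have different viral loads from first infections in seronegative participants. A reader of the results could not separate them, and the table could not properly be reported as primary endpoint 2. A smaller matter is that Immediate-arm infections before any dose would appear in the Immediate row unmarked, although SAP 7.1 and 7.2 separate exposure by doses received.

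**Working it through.** **1. The sections side by side**

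| Place | Population for viral load |
|---|---|
| SAP 2.2, primary endpoint 2 | Infected participants seronegative at enrollment |
| Protocol section 6, introduction | Main study participants seronegative at enrollment |
| SAP 3.1, primary analyses | Baseline SARS-CoV-2 negative set, enrolled as randomised |
| SAP 3.1, FAS-P | Secondary data set |
| SAP 2.2, secondary objective 5 | All enrolled, any baseline serostatus |
| SAP 7.3 | FAS-P only |

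The disposition table in SAP 5.1 splits FAS participants with study PCR into four baseline groups: seropositive, no qualifying serostatus, seronegative but PCR positive, and negative on both tests. Only the last group forms the Baseline SARS-CoV-2 negative set; FAS-P includes all four. The SAP 7.1 incidence table is also descriptive, yet it is produced in both sets.

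**2. The plan's own figure.** SAP 2.5 gives 96.9% power for a 1-log difference, with 225 events, SD 1.8 and a one-sided 0.025 test. Vaccine efficacy (VE) of 50% splits the events 150:75. The standard error is 1.8 × √(1/150 + 1/75) = 0.2546. Then 1/0.2546 − 1.96 = 1.968, which gives 97.5% (97.4% with the noncentral t). This agrees with the simulated figure. The 225 events were counted among baseline seronegative participants, so the design had the restricted population in mind.

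**3. How much baseline positives could contribute (illustration).** Inputs: 10% baseline seropositive (Protocol Table 6-2), 112 days of follow-up (Day 1 to Day 113), and SAP 3.2.2, under which a baseline-positive participant can have an incident infection only from 90 days after the first swab. I assume equal infection risk while at risk.

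- Rule applied to all baseline positives: 0.10 × 22 / (0.10 × 22 + 0.90 × 112) = 2.2/103 = 2.1% of at-risk time.
- Rule applied to none: 10%.
- With 5% to 30% baseline positives: 1.0% to 7.8% with the rule, 5% to 30% without it.

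Which case applies is unclear. SAP 3.2.1 delays the start of study time only when the first swab is positive, whereas 3.2.2 applies the 90 days to seropositives as well. Unknown-serostatus participants come on top, and their number is not given.

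**4. Immediate-arm infections before dose 1 (illustration).** Protocol Appendix I allows about 7 days for post-enrollment activities. I assume that every Immediate participant swabbed for 7 days before dose 1, that the hazard is constant, and that there is no efficacy for 14 days after dose 1. The share is 7 / (7 + 14 + (1 − VE) × 91):

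- VE 50%: 7/66.5 = 10.5%
- VE 70%: 7/48.3 = 14.5%
- VE 90%: 7/30.1 = 23.3%

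SAP 3.1 says only that some participants swabbed early, which would lower these shares; delays longer than 7 days would raise them.

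**The case against.** The strongest reply is that SAP 3.1 expressly lets FAS-P participants supply viral-load data, so FAS-P is a permitted set. The study stopped early, SAP 2.4 treats analyses of randomised participants as post-hoc, and 7.3 plans no test, interval or estimated difference. All of that stands and limits the consequence. It does not explain why the required set is missing: low power is a reason to drop inference, not to change the population without comment.

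A reader might infer that tabulating by arm uses the wrong exposure. The documents do not support this. SAP 3.1 prescribes analysis by enrollment group, and Protocol 6.4.4 plans the peak comparison between the Immediate Vaccination and Standard of Care arms. The supportable point is narrower: 7.3 lacks the breakdown by doses received that 7.1 and 7.2 provide.

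A reader might also infer that a true 1-log effect would be diluted by a definite amount. The documents do not give the share of infections before dose 1, and the table is on the CT scale, so any log figure would be illustrative only.

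Nor does the enrolled-as-randomised restriction alter much by itself. In a by-arm table, Vaccine Declined participants would be a separate row. But 7.3 does not say whether that row is shown, and SAP 7.1 calls that group an arm too.

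**Conclusion.** The point holds as an omission and an internal inconsistency. If 7.3 is followed as written, primary endpoint 2 is not produced in its stated population, and only its any-serostatus counterpart is reported. This rests on the text alone and needs no numerical assumption.

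The size of any distortion cannot be computed from the documents. The shares above depend on the stated assumptions, and the baseline-positive share may be as low as about 2%. Because the analysis is openly descriptive, the consequence is modest. The change should still be made, since FAS-P already contains the required participants. The missing dose split is a secondary point.

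**What to change.** In SAP 7.3, produce the peak CT table and the days-positive table first in Baseline SARS-CoV-2 negative participants enrolled as randomised, Immediate versus Standard of Care. Then repeat both in FAS-P, labelled secondary, as 7.1 does. State which groups appear in each table. Keep the tabulation by arm. Add a supplementary breakdown of Immediate-arm infections by study doses received at the first positive swab (0, 1, 2). Reconcile 3.2.1 with 3.2.2 on whether the 90-day rule covers seropositive participants whose first swab is negative.

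If the sponsor intends FAS-P as the only set for viral load, SAP 3.1 should be amended to say so, with a reason, and the result reported as secondary objective 5.

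The cost is a few lines of SAP text and extra tables from data already held. The downside is sparse cells, since peak CT is already split by lab, target and arm. The dose breakdown could therefore be given as counts where cells are very small.

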An additional potential indirect effect of a vaccine is its effect on reducing secondary transmission of infection, written VE_I and defined as the multiplicative reduction in the rate of secondary transmission among vaccine vs. placebo individuals who become SARS-CoV-2 infected. A vaccine might reduce transmission through reducing the magnitude and/or duration of viral shedding, by reducing symptoms associated with transmission such as coughing, or by selectively blocking infection with less transmissible viral strains. Evaluating the effect of a COVID-19 vaccine on transmissibility is critical because a vaccine with high efficacy against COVID-19 disease but low efficacy against SARS-CoV-2 infection would necessarily yield a net increase in the number of asymptomatic infections. If individuals who become asymptotically infected despite having received the vaccine are still infectious, and given that asymptomatic individuals are less likely to be diagnosed and self-isolate, such a vaccine has the potential to increase transmission and prolong the pandemic (2, 3).

As we prepare this study, we recognize there are other approaches to measuring population level benefit (eg, vaccine effect on infection and transmissibility). These approaches include: observational studies, such as those being conducted in Israel to examine population benefit of the vaccine and those planned by the CDC to examine transmission from vaccinated individuals to household contacts in longitudinal cohorts; and ancillary studies with frequent swabbing on a subset of participants in Phase 3 studies. However, none of these studies will allow for the rigorous capture, through daily nasal swabbing, of the early dynamics of viral replication and the capture of transmission events during the acute period of infection in a randomized trial.

All of these vaccine salutatory effects may depend on a variety of individual characteristics such as age, prior infection with SARS-CoV-2; on virological characteristics; and in the case of VE_I which conditions on infection, may depend on clinical characteristics such as symptomatology.

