Appendix F Procedures for Main Cohort, Standard of Care and Vaccine Declined Groups

Visit: Day: Week: Month: Procedure	01 ¹ Scr.	02 D1 W0 M0	03 D29 W4 M1	04 D57 W8 M2	05 D113 W16 M4 VAC1	06 D141 W20 M5 VAC2
Study procedures						
Screening consent (if used)	✓	–		–	–	–
Assessment of understanding	✓	–		–	–	–
Protocol consent (eConsent)	✓	–		–	–	–
Medical history questionnaire ²	✓	✓		–	–	–
SARS-CoV-2 infection risk assessment ²	✓			Weekly		–
COVID-19 symptom surveillance ²	–			Weekly		–
Confirm eligibility	✓	–		–	–	–
Obtain demographics ²	✓	–		–	–	–
Randomize, Standard of Care Group only	–	✓		–	–	–
SARS-CoV-2 testing questionnaire ²	–			approximately 2x per week		–
End of study questionnaire ²	–	–		–	✓ ⁷	✓
Research Samples						
Serum for SARS-CoV-2 clinical serology ³	–	✓		✓	✓	–
Nasal swab	–			Daily ⁴		–
Vaccination procedures⁶						
COVID-19 symptom check ⁵	–	–		–	✓	✓
Vaccination	–	–		–	✓	✓

Greyed out visit does not apply to this group.

1 Screening may occur over the course of several contacts/visits up to and including day 1, prior to randomization.

2 Results from screening at school, if applicable, or at other locations will be captured via eDiary, please see Section 9.16.

3 From screening to the final study visit, the total blood volume to be collected from each participant will be approximately 15 mL (maximum) with a maximum of approximately 5 mL collected in a single visit. For blood self-collected by a participant the maximum volume will be less than 1 mL in a single collection. If a Main cohort participant is also in the Prospective Close Contact (PCC) cohort related to an index case or in the Case-ascertained Close Contact (CACC) cohort, one additional blood collection (self-collection) will be performed (see table below).

4 Daily swabs will be collected from D1 through D113. Swabs will be returned via drop-off location(s) specified by the clinic or through the mail.

5 COVID-19 Symptom Check to be performed within 24 hours prior to vaccination.

6 Vaccination procedures only apply to participants who have not received COVID-19 vaccine outside the study and for participants in the Vaccine Declined Group who request to be vaccinated.

7 Only applies to participants who are not receiving vaccination on study, ie, who have already received COVID-19 vaccine outside the study or who have declined vaccination (Visit 5 will be the last study visit for these participants).

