3.2.6 SARS-CoV-2 exposure

Given the open-label nature of the study, it is possible that individuals in the Immediate Vaccination, SoC, and Vaccine Declined groups have different exposure to SARS-CoV-2. While the randomized groups are ensured to balance with respect to baseline factors, individuals in the Vaccine Declined Group are likely to differ from those in the randomized groups based on both baseline and time-varying factors related to exposure. Imbalanced exposure between groups may lead to bias in analyses that compare endpoint distributions between groups. A series of analyses will explore predictors of SARS-CoV-2 exposure based on baseline SARS-CoV-2 negative participants in the SoC group. Separate but identical analyses will explore predictors of exposure in the Vaccine Declined group.

The outcome of interest will be time to incident infection. Calendar time will be the time scale and participants will be censored using 'outside testing censoring'. Baseline and time-varying variables listed above in Section 3.2.5 will be screened univariately for their associations with SARS-CoV-2 infection based on Cox proportional hazards models that stratify on study site. Variables with p-values less than 0.10 will be retained. Retained baseline variables will be screened further to remove highly correlated variables; for pairs with absolute value of Spearman correlation > 0.90 , a randomly chosen member of the pair will be retained. Cox regression with lasso penalty, stratified on study site and implemented with glmnet and with the retained variables from the previous step, will be used to derive a 'risk score' that is used for

adjustment in multiple analyses described below. The linear predictor of the penalized Cox model will be used as the risk score. This risk score will be included as a covariate in efficacy analyses described in Section 7.

3.2.7 *Noncompliance with swabbing*

Noncompliance with daily nasal swabbing may result in missed endpoints and incompletely observed viral load trajectories.

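### SAP 7.3 drops every participant with CT values from both labs; this may remove longer shedders, possibly unequally by arm, and neither a count of exclusions nor a table retaining them is planned

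*SAP*

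**What the plan says.** SAP 7.3 is the only analysis this SAP gives for primary objective 2. It explains that early termination left the study underpowered for viral load and continues: "Therefore a limited, descriptive analysis will be performed". Peak CT is tabulated by lab, target (N1, N2) and arm among infections in the FAS-P set, censored at outside vaccination. "Peak viral load will be defined as the minimum observed CT per participant, lab and target". The next sentence is the exclusion: "Participants with CT data from both labs will be excluded". The reason given for separating the labs is attached to stratification and not to the exclusion: "Results are stratified by lab to address potential differences between labs".

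The same section also plans "descriptive statistics for the number of days with a positive study PCR (qualitative) per participant among FAS-P acquisitions, broken down by arm", with no both-lab exclusion stated for it.

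One infection can yield many CT values. For the Standard of Care and Vaccine Declined groups, Protocol Appendix F says "Daily swabs will be collected from D1 through D113"; Appendix E has daily swabs to the same day for the Immediate Vaccination Group. Neither document says how swabs were allocated to labs: by swab, by site or by calendar period.

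**The concern.** The exclusion acts on whole participants and depends on something observed after infection. Unless one specimen was run at both labs, CT data from both labs needs at least two CT-yielding swabs. The more such swabs a participant has, the more chances to appear at both. Shedding length is itself an outcome of interest: Protocol 2.2 says "A vaccine might reduce transmission through reducing the magnitude and/or duration of viral shedding", and duration is part of secondary endpoint 4. The number of CT values also depends on adherence, since SAP 3.2.7 notes that "Noncompliance with daily nasal swabbing may result in missed endpoints and incompletely observed viral load trajectories".

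If the arms differ in shedding length or in swabbing, they can lose different fractions of cases. If peak and duration are also correlated, the cases left are not representative in peak CT. Protocol 6.4.4 already treats post-randomization selection as the main threat to the conditional viral-load comparison, and this rule adds a second selection step. The per-lab definition and lab stratification already keep CT values from different labs apart, so the stated worry about lab differences does not by itself require the exclusion.

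At stake is a descriptive table for a primary objective, in a study that can ill afford to lose infected cases.

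**Working it through.** **Plan's own figure.** Protocol 6.1.1 states 96.9% power for a 1-log10 reduction with SD 1.8, 225 events and VE 50%, one-sided 0.025. Protocol 6.1 puts 75 of the 225 events in the vaccinated group, leaving 150. The noncentrality is 1 / (1.8 × √(1/75 + 1/150)) = 3.93 on 223 df, giving 97.4%. The stated figure is reproduced within simulation error and is not in dispute. The SD and effect size are used again below.

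**Chance of exclusion given k CT-yielding swabs, each run at one lab.**
- Swab-by-swab routing, fraction q to the second lab: 1 − q^k − (1 − q)^k.
- One calendar switch of lab in a window of W = 112 days, consecutive daily swabs: (k − 1)/W.
- Lab fixed per participant: 0.

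| Routing | k=1 | k=2 | k=5 | k=10 |
|---|---|---|---|---|
| q = 0.05 | 0 | 9.5% | 22.6% | 40.1% |
| q = 0.10 | 0 | 18.0% | 41.0% | 65.1% |
| q = 0.20 | 0 | 32.0% | 67.2% | 89.3% |
| One switch in 112 days | 0 | 0.9% | 3.6% | 8.0% |

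The chance never falls as k rises.

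**Effect on the arm difference, CT scale (all inputs assumed).** Positive days are log-normal, median 9 (SoC) and 6 (vaccinated), log-SD 0.5. Peak CT has SD 5 and a true difference of 2.0 CT, with longer shedders having lower CT at correlation ρ. One million cases per group:

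| Routing | Excluded SoC / vaccinated | ρ = 0 | ρ = 0.3 | ρ = 0.6 |
|---|---|---|---|---|
| q = 0.05 | 39% / 28% | 2.0 | 1.9 | 1.8 |
| q = 0.10 | 61% / 48% | 2.0 | 1.8 | 1.6 |
| q = 0.20 | 84% / 72% | 2.0 | 1.7 | 1.4 |
| One switch in 112 days | 8% / 5% | 2.0 | 2.0 | 1.9 |

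Capping CT at 39 can move the lowest entry to 1.5.

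**Same check on the protocol's scale.** SD 1.8 and a true difference of 1.00 log10 are taken from the protocol; mean positive swabs of 10 (unvaccinated) and 5 (vaccinated) are assumed.
- q = 0.05 excludes 38% and 22%; the difference is 0.99, 0.94 and 0.89 at ρ = 0, 0.3 and 0.6.
- q = 0.10 excludes 61% and 38%; the difference is 1.00, 0.91 and 0.81.
- One switch excludes 8.0% and 3.6%; the difference is 0.97 to 0.99.
- With equal swab counts (10 and 10), exclusion is equal and the difference stays at about 1.00 for all these routings.

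**Cost of retaining both-lab cases under the lab of their first positive swab.** This needs an assumed CT curve. A triangular curve was used: CT 40 at the ends, peak 30% of the way through the positive days, mean SoC peak CT 22 or 25. The peak of both-lab cases is then missed by about 1.4 to 2.5 CT on average, in both groups. The arm difference comes out at 1.9 to 2.1 across all q and ρ shown. At ρ = 0 and q = 0.05 or 0.10 this is slightly worse than exclusion (1.9 against 2.0). Other curve shapes can give values down to about 1.8.

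**The case against.** Excluding both-lab participants is a defensible choice. Each lab's minimum covers only part of such a person's trajectory and may not be the peak. Listing the person under each lab counts them twice, and a minimum across labs mixes CT scales. All of this stands. It is why the retained version should sit beside the exclusion version and not replace it.

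The premise that a swab has CT data from one lab only is itself an assumption. The documents do not rule out retesting of one specimen at both labs, in which case a single-swab case could be excluded too. That also stands, and it is a reason to state the routing.

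The table is descriptive, with no test or effect estimate, and SAP 2.4 treats the randomized analyses as post hoc. It is laid out by arm, and SAP 3.1 says some Immediate Vaccination participants accrued follow-up and events before their first dose, which weakens any arm contrast in shedding. This limits the consequence.

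The loss is partly visible already. The peak table reports N, SAP 7.1 tabulates FAS-P infections by group, and positive days are summarised by arm. But the shortfall read off this way would mix both-lab exclusions with infections that have no CT value, so it does not replace a direct count.

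**Conclusion.** The point holds in limited form. If each swab is run at one lab, exclusion becomes more likely with more positive swabs. The rule may therefore remove longer shedders, possibly unequally by arm, and the SAP plans neither a direct count nor an analysis that keeps them.

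A reader might go further and infer that long and heavy shedders are removed more often among the unvaccinated, so that the vaccine effect is understated. The documents do not support that. Heavy shedders go preferentially only if peak and duration are correlated. Unequal loss against the unvaccinated needs a vaccine effect on duration, which the protocol offers only as a possibility, together with similar swabbing and routing in the arms.

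The size runs from negligible (one calendar switch of lab, or no correlation) to material. Under swab-by-swab routing at correlation 0.6, the assumed 2.0 CT falls to about 1.8, 1.6 and 1.4–1.5 as q goes from 5% to 20%. At correlation 0.3 it falls to 1.9, 1.8 and 1.7. Where these conditions hold, the arm difference is understated. For a descriptive table this is a cheap improvement worth making.

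**What to change.** In SAP 7.3:
- State how swabs were routed to labs.
- Report the number of infected participants with CT data from both labs, by arm.
- Tabulate peak CT with these participants retained under the lab that ran their first positive swab, using the minimum CT from that lab's swabs only.
- Show this alongside the version that excludes them.

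The cost is a few sentences and one additional table. The downside is that the retained participants' peak may be under-observed, which in most settings examined slightly attenuates the difference. Neither version is clean alone, so both should be shown. If they agree, or if the both-lab count is small and similar across arms, the question is closed.
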